5.3 Safety Evaluations

Falls are inherent in healthcare settings and cannot be entirely eliminated. As such they are not an adverse event arising from or related to the use of the Palarum PUP™ System.

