SECONDARY OBJECTIVES	
 1. To reduce the incidence of false alerts, <5%. Our goal is a high reliability notification system. 2. To provide positive alert reliability of 95%. Our goal is to reduce alert fatigue with nurses. To determine number of alerts sent out; what is the frequency of these patient safety events (i.e.), fall risk patient up, out of bed, unassisted 3. To gather compliance data and response times from alert to caregiver response.
NUMBER OF SUBJECTS	2500 patients
SUBJECT SELECTION CRITERIA	
Inclusion Criteria: All risk fall patients, eighteen years of age or older, who are admitted to the OSU Brain and Spine Hospital on Floors 8 South, 9 South, 10 South, 8 East, 9 East or 10 East. Patients will undergo a pre-assessment as per OSUWMC procedure to determine if they are of fall risk.
 
Exclusion Criteria: Patients whose medical condition as assessed by the PI prohibits their participation in the program, which would include among others the following: patients who lack the capacity to consent that do not have an Legally Authorized Representative (LAR), patients with an anatomy or wound issue on their feet or around their calves that would bar them from wearing socks on either foot, and/or patients for whom the sock would impede medical treatment.

TEST PRODUCT, DOSE, AND METHOD OF USE	
Test Product: Palarum LLC's, PUP™ (Patient is Up) System
 
Dose: N/A
 
Method of Use:
 
The Study site, the OSU Wexner Center Brain and Spine Hospital, is located on three contiguous floors with each floor being made up of two units or Pods designated East and South. Following commencement of the study, and throughout its duration, Pods assigned to the Study will only utilize the Palarum Fall Prevention System and a monitored PUP™ sock as the standard of care intervention for fall prevention in accordance with its operating instructions and procedures. The Implementation Team for the Study will consist of the PI, the Nurse Managers and Staff, allied health professionals as may be assigned to the Pods during the course of the Study.
 
The Palarum Fall Prevention System is made up of seven tangible elements connected by Wi-Fi and/or BTLE: an inpatient room

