--	---

	
utilizing the IRT. All patient relevant fall data, including system performance, is collected and stored in the PCS for future study and evaluation. Any patient fall is to be reported and evaluated following current OSU Medical Center processes and procedures independent of the Palarum Fall Prevention System.
 
Technical support for the Palarum Fall Prevention system is available by phone at [name] [contact] and email, [contact], 24x7. If there is a Palarum Fall Prevention System outage each Intervention Group Pod should follow policies related to downtime procedures for fall risk patients.

CONTROL PRODUCT, DOSE AND ROUTE OF ADMINISTRATION	N/A
DURATION OF SUBJECT PARTICIPATION AND DURATION OF STUDY	Duration: Once a patient has been placed in the fall risk protocol, the patient will remain in the study until a nurse removes the patient from risk fall status or the participant has been discharged from the hospital.
CONCOMITANT MEDICATIONS	
Allowed: YES
 
Prohibited: NONE

EFFECTIVENESS EVALUATIONS	
Effectiveness evaluation data will be collected by the Palarum Fall Risk System, and incorporated and integrated with patient diagnosis, co-morbidities, and other medical data within REDCap including:
 
 1. Enrollment Data 
 a. Patient Identifier/MRN b. Patient Weight c. Patient Sock Size (S-M-L-XL) d. Sex e. Pod and Room/Bed f. Date g. Time h. Sock Number i. Sensor Number 2. Event Logs 3. Time of stand alert 4. Time to clear 5. Who cleared stand 6. Manual or Automatic termination 7. Accelerator and Gyroscopic Data surrounding each stand event

	8. Pressure on foot 9. Motion of patient
PRIMARY ENDPOINT	Fall rate per patient days within the study sample population
SECONDARY ENDPOINTS	
As collected by the Palarum Fall Prevention System, validated by manual audits of thereof, and integrated with REDCap,
 
 • Rate of false alerts • Rate of fall related patient safety events • Time to respond to alert • Pressure on foot • Motion of patient • Alert fatigue analyzed and measured by alert responded/alerts generated over time. • Notification system alerts only the closest five caregivers when a fall risk patient is up • Time to staff notification (latency) when a fall risk patient is up and unattended • Time to clear data • Identification of caregiver clearing alert • Determination of manual or automatic termination

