2.1 Risk / Benefit Assessment

Risks of Product

- Over-reliance on automation of technology decreasing hourly rounding presence
- System fails to notify staff of stand alert
- Possible skin impression from prolonged use of sock

Mitigation of Each Risk

- Education
- Patient Assessments
- Replacement of Socks
- Socks come with multiple locations with sock sensor placement

Benefits

- Improved patient safety by reducing the number of patient falls. A 25% reduction in patient falls will result in 90 less falls per year in a 200-bed hospital.
- Improved patient outcomes
- Staff is notified immediately when a patient safety event occurs (fall risk patient is up and unattended)
- Reduced alert fatigue. Improved accuracy of the stand detection with innovative pressure sensitive smart textiles. New notification system which alerts only the closest five caregivers, with an escalation protocol, when a fall risk patient is up and automatically terminates the alert when a caregiver enters the room.
- Data & Analytics. The PUP™ Fall Prevention System delivers critical new data to enhance patient care and improve hospital operations.
- Cost Savings. The Palarum LLC, alert system could save one 200 bed hospital approximately \$744,600 dollars each year. Average 200 bed hospital is expected to have 5 patient falls per 1000 patient days. Therefore, an average 200 bed hospital will have 365 falls per year (20% reduction in patient falls (73)/year x \$10,200/ fall).

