10 ADVERSE EXPERIENCE REPORTING AND DOCUMENTATION

10.1 Adverse Events

An Adverse Event has to meet three basic criteria to be reportable; an AE has occurred, the device is associated with the AE and the AE led to 1 of 4 outcomes: decline in state of health of patient, threat to public health, could lead to death or serious injury if it occurs.

The Investigator will probe, via discussion with the subject, for the occurrence of AEs during each subject visit and record the information in the site's source documents.

Adverse events will be recorded in the patient CRF. Adverse events will be described by duration (start and stop dates and times), severity, outcome, treatment and relation to study, or if unrelated, the cause.

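### Section 5.3 rules every fall unrelated to the device in advance, which conflicts with the product risks in 2.1 and the event-level relation field in 8.6 and 10.1

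*Protocol*

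**What the plan says.** Protocol 5.3 (Safety Evaluations) has two sentences. The first says that falls are part of healthcare and cannot be fully eliminated. The second draws the conclusion: "As such they are not an adverse event arising from or related to the use of the Palarum PUP™ System". No exception is given.

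Protocol 2.1 (Risk / Benefit Assessment) lists these among the risks of the product:
- "System fails to notify staff of stand alert"
- "Over-reliance on automation of technology decreasing hourly rounding presence"

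The synopsis gives one safety evaluation, the incidence of adverse events arising from use of the device. Section 10.1 makes an event reportable only if, among other conditions, "the device is associated with the AE". The same section asks that each event be described by, among other items, "treatment and relation to study, or if unrelated, the cause". Section 8.6 also asks for relation to study.

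On how the system is used, the synopsis (Method of Use) says study pods "will only utilize the Palarum Fall Prevention System and a monitored PUP™ sock as the standard of care intervention for fall prevention". It foresees system failure ("If there is a Palarum Fall Prevention System outage") and in the same sentence sends pods to their downtime policies for fall-risk patients. On fall reporting it says: "Any patient fall is to be reported and evaluated following current OSU Medical Center processes and procedures independent of the Palarum Fall Prevention System".

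**The concern.** Section 5.3 settles a causal question for a whole class of events before any has occurred. A background rate makes it hard to say whether a particular fall was caused by the device. It does not show that no fall can be.

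The protocol itself names two ways in which the product could contribute to harm: staff are not told that the patient is standing, or they round less because they trust the system. In a study of a fall-prevention device on fall-risk patients, the obvious harm from either is a fall. The hazards are acknowledged in 2.1 and their most likely consequence is declared unrelated in 5.3.

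What is at stake is the meaning of the safety result. If 5.3 is followed, a statement that no device-related falls occurred reflects the classification rule and says nothing about the device.

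**Working it through.** The point rests on no sample size, power or rate, so there is no planned figure to reproduce. The check sets the passages side by side.

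**1. Scope of the rule.** Section 5.1 defines a fall broadly: assisted or unassisted, with or without injury, physiological or environmental. Section 5.3 speaks of falls without qualification, so it covers all of them.

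**2. Link to the listed risks.** 2.1 names a failed alert and reduced rounding. It does not name a fall as the resulting harm; that step is an inference, but a short one. 2.1 names a failed alert and not a late one, but 5.3 would cover a fall after either. The mitigations in 2.1 (education, patient assessment, sock replacement, sensor placement) may make such events rarer. They do not bear on how a fall is classified.

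**3. Route into the safety result.** The synopsis counts adverse events arising from device use. Section 10.1 requires a device association. Section 5.3 says that no fall has one. Taken together, no fall can qualify, whatever its seriousness.

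**4. The opposing instruction.** Sections 8.6 and 10.1 call for relation to be recorded event by event, and 10.1 asks for a cause when an event is unrelated. An investigator could record a relation for a fall under these sections and contradict 5.3 in doing so. The protocol does not say which prevails.

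**5. Whether another route restores attribution.**

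| Route | Captures the fall? | Attributes it to the device? |
|---|---|---|
| Primary endpoint (5.1, 13.2) | Yes, all falls | No; it is a total rate against a historical rate |
| Serious events (10.2, 15.2) | Yes, if serious, regardless of causality | No |
| Investigator duties (15.5, items 4 and 8) | Adverse events go to the sponsor; unanticipated problems go to the IRB and sponsor | Not by themselves |
| Hospital fall process (synopsis) | Yes | Not stated; described as independent of the system |
| Alert reliability, latency and response time (synopsis, 5.2) | Not falls; they measure alert performance | No link to individual falls is described |

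No route both captures a fall and assigns it to the device.

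**6. Size.** The rule covers 100% of falls. At the plan's own rates (13.2, 13.4) the class runs from 0.004 × (1 − 0.25) = 0.003 to 0.004 per patient-day, or 3 to 4 falls per 1000 patient-days. The documents do not say what share would follow an alert failure or reduced rounding, and the point does not depend on it. The SAP reports 0 falls, so the number actually left out of the device-related result is 0.

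**The case against.** The strongest reply is that falls are the primary endpoint. Harm from missed alerts would raise the fall rate, and keeping efficacy events out of the adverse-event tables is a common design preference. Serious events are documented and sent to the IRB whatever their cause, and 15.5 adds further reporting duties. Reporting falls independently of the device can be a strength, because ascertainment then does not rely on the product under test. Outages have downtime procedures. The SAP reports 0 falls.

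Much of this stands. Falls are not lost to the study, and the plan also set out to measure alert performance directly. But a convention that endpoint events are tabulated separately would say only that. Section 5.3 goes further and makes a statement about causation. A total rate cannot attribute individual falls, and a net reduction could coexist with some falls that followed a failed alert.

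Four stronger readings are tempting and are not supported:
- *A null result on device-related falls is guaranteed.* The relation item in 8.6 and 10.1 remains, and precedence is not stated. The result follows if 5.3 is applied as written.
- *Section 5.3 also excuses alert failures.* It speaks of falls only. An alert failure itself is not ruled unrelated and could be reportable under 10.1.
- *Patients are left without fall precautions in an outage.* The sentence that mentions outages also refers to downtime policies.
- *The rule explains the SAP's zero.* Section 5.3 governs classification as an adverse event and removes no fall from the primary count.

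Nor is the loss confined to minor falls, as a reader might infer from the serious-event rules. Those rules record serious falls but do not restore attribution to the device.

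**Conclusion.** The point holds as a conflict to be reconciled: 5.3 against 2.1, and 5.3 against 8.6 and 10.1. Applied as written, 5.3 keeps every fall, serious or not, out of the device-related adverse-event result, and the absence of device-related falls would then be uninformative.

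This rests on two assumptions: that 5.3 is followed where it collides with the relation item, and that a fall is a plausible harm of the two risks in 2.1. What is lost is attribution to the device; the falls themselves are still counted. The primary analysis is untouched and no reported result changes. The defect is moderate and cheap to correct, and should be corrected.

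**What to change.** Replace the second sentence of 5.3 with: *Falls are not presumed to be related or unrelated to the PUP System; relatedness is assessed and recorded for each fall.* Align 2.1, 8.6 and 10.1 with it, and state that the recorded relation includes relation to the device. Then:

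- Include falls judged device-related in the safety result.
- For each fall reported through the hospital process, consult the cloud service's alert and notification records, where available, to see whether an alert was generated and delivered, and when. These records can inform a judgement on failed or late alerts. They cannot show reduced rounding, so over-reliance needs a separate judgement.
- List falls whose relation cannot be determined, and do not count them as unrelated by default.

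The cost is a one-sentence amendment with matching edits and a short review per fall. Some events may be reported as device-related. Some falls may stay undetermined: the synopsis says that alerts and notifications are recorded, but the SAP's event dataset lists no alert-delivery field, and the SAP states that no data were collected for the alert-reliability objective. The reported 0-fall result would not change.

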6 SUBJECT SELECTION

6.1 Study Population

- All fall risk patients, eighteen years old or older, admitted to the OSU Medical Center Brain and Spine Institute on Floors 8, 9 and 10. “Fall risk” will be defined by OSUWMC standard of care criteria.

6.2 Inclusion Criteria

- Written informed consent obtained from subject (and/or LAR) and ability for subject to comply with the requirements of the study.
- All fall risk patients, eighteen years old and older, on Floors 8, 9 and 10 of the OSUWMC Brain and Spine Hospital, with “fall risk” as defined by OSU criteria, for whom no medical condition prohibits their participation in the program, (see Exclusion Criteria).

6.3 Exclusion Criteria

- Presence of a condition or abnormality that in the opinion of the Investigator would compromise the safety of the patient or the quality of the data.
- Patients whose medical condition prohibits their participation in the program, which would include among others, patients with an anatomy or wound issue on their feet or around their calves that would bar them from wearing socks on either foot, and/or patients for whom the sock would impede medical treatment.

7 STUDY TREATMENTS

7.1 Method of Assigning Subjects to Placebo or Test Evaluation Groups

Eligible patients will be enrolled in the PUP™ System treatment. Pod staff will assess fall risk and study team will determine eligibility.

7.2 Formulation of Test and Control Products

Palarum, LLC manufactures the socks and provides the equipment.

7.3 Packaging and Labeling

The PUP™ System socks will be provided individually wrapped in a plastic package.

Each pair of socks will be labeled with a unique number and each package will be labeled with the name of the sponsors, and directions for patient use and storage. (Appendix A)

7.4 Supply of Study Socks and Equipment at the Site

All socks for patients admitted to study will be stocked in the respective floors supply closet with their existing socks. All equipment for the study patients will be in place and tested before the study begins.

7.5 Regimen

Each patient will be fitted with a sized pair of PUP™ socks and enrolled in the system. Socks will be worn continuously throughout the stay unless soiled or identified as defective by the self-testing of the PUP™ System. If soiled or defective, the socks will be replaced from the supply.

7.6 Dispensing

All fall risk candidates who provide consent will be enrolled by the caregiver or CRC into the PUP™ Fall Risk Solution upon enrollment.

7.7 Administration Instructions

- Nurse will enroll the patient.
- Sock is fitted to patient.
- Patient anatomy and foot size will determine the selection of appropriate sock size.

- Series of 5-7 dots (size dependent) on top of sock will be aligned with center of foot.

7.8 Supply of Study Inventory at the Site

- Appropriate sizes will be stored in a supply cart on the unit.
- Sock inventory will be maintained

7.9 Storage

Storage of the PUP™ S equipment will be within the Brain and Spine Hospital.

7.10 Study Accountability

- Upon discharge, the patient will be un-enrolled from the PUP™ Fall Prevention Solution.
- Socks will be put in a special recyclable bin that will be returned to the vendor to be laundered and inspected for quality assurance.
- An accurate and current accounting of the dispensing and return of PUP™ socks for each subject will be maintained on an ongoing basis by a member of the study site staff.

7.11 Measures of Treatment Compliance

- Each morning at 12am a report will be generated detailing the previous day's activity on the system.
- Two separate reports will be sent each morning at 12am (filtered by audience): Nurse Manager, Site Executive.
- The reports will show:
 - The Pod where the patient is enrolled
 - # of alerts during their length of stay
 - Whether a patient has alerted 3 or more times in less than 24 hours.

8 STUDY PROCEDURES AND GUIDELINES

- A Schedule of Events representing the required testing procedures to be performed for the duration of the study is diagrammed in (Appendix B).
- Prior to conducting any study-related activities, Pod staff will identify eligible patients and notify study staff to consent and enroll. Written informed consent and the Health Insurance Portability and Accountability Act (HIPAA) authorization must be signed and dated by the subject or subject's legal representative.

8.1 Clinical Assessments

Clinical assessment of foot and ankle

8.2 Concomitant Medications

All concomitant medication and concurrent therapies will be documented at Baseline/Screening, at early termination when applicable and at discharge. Dose, route, frequency of administration, and indication for administration and dates of medication will be captured.

8.3 Demographics

Demographic information (date of birth, sex, race) will be recorded at Baseline Screening and again at enrollment in the PUP™ System.

8.4 Medical History

Relevant medical history, including history of current disease, other pertinent history, and information regarding underlying diseases will be recorded at Baseline Screening.

8.5 Physical Examination

Clinical assessment of foot and ankle

8.6 Adverse Events

Information regarding occurrence of adverse events will be captured throughout the study. Duration (start and stop dates and times), severity/grade, outcome, treatment and relation to study will be recorded on the case report form (CRF – Appendix C).

9 EVALUATIONS BY VISIT

9.1 Pre-Conditions

- All nurses/applicable staff trained on Palarum PUP™ System
- All equipment installed in rooms
- At beginning of shift nurses wearing smart notification devices & enrolled into unit.

9.2 Day 1 – Admission

- Patient Admission
 - Patient admitted into a room with the Palarum PUP™ technology
- Fall Risk Screening
 - Patient undergoes fall risk assessment.
 - If patient is determined to be fall risk they proceed to next step
- Registration into Study
 - Dedicated trained staff will be notified and will enroll the Patient into the Study as soon as medically feasible and reasonable.
 - If patient is determined as candidate for study, they are registered as a study participant.

- Review the study with the subject and obtain written informed consent and HIPAA authorization and assent, if appropriate.
- Assign the subject a unique screening number.
- Record demographics data.
- Record concomitant medications.
- Patient Education
 - As noted in “Pre-Conditions” all nursing and related staff are trained on how to use the Palarum Fall Prevention Technology before the study starts.
 - Continuous training will be available for new staff through Buckeye Learn.
- Fit with Sock
 - Upon registration into this study, the patient will be fitted for a PUP™ sock by the nursing staff.
 - Nursing staff utilizes a sizing chart to correlate patient’s foot size with PUP™ Sock size.
 - Sock is placed on patient
- Enroll Sock in Application
 - Once sock is successfully fitted on patient the nurse proceeds to enroll the patient through Palarum Application.
 - The following categories must be completed before proceeding to a successful enrollment: Patient Name/Initials/MRN, Sex, Weight, Sock Size, and Sensor.
 - Upon successful sock pairing to IRT the enrollment process is completed, and the patient is now being monitored.

9.3 Day 1 through length of stay

- System will electronically monitor patient compliance
- Report Generation
 - Each morning at 12am a report is generated detailing the previous day’s activity on the system.
 - Two separate reports are sent each morning at 12am (filtered by audience): Nurse Manager, Site Executive.
 - The reports show: the Pod the patient is enrolled in, # of Alerts during their length of stay, whether a patient has alerted 3 or more times in less than 24 hours
- Alert Generation
 - An alert is generated when a patient places their foot on the ground and takes a step.
 - False alerts are prevented through the use of a gyroscope and accelerometer.
 - Once an alert is generated it is sent to the IRT, HUC, and Smart Notification Devices.
- How to respond to Alerts
 - There are two ways to respond to an alert with Palarum’s Fall Prevention System

- Nurse proceeds into the room (wearing Palarum Smart Notification Device) and the system automatically turns off due to his/her proximity.
- Nurse proceeds into the room and manually turns off the system on the IRT by touching the red alert icon on the screen and then entering their initials.
- Documentation of exceptions.
- Record any Adverse Experiences and/or Review subject diary for adverse experiences and compliance.
- Perform clinical examination of foot and ankle.

